7.10.3. Secondary Efficacy Analyses

Secondary efficacy analyses common to all ISAs within CPMP have been described in the CPMP SAP Version 5. Unless otherwise specified, the time point for secondary endpoint measurements is the same as that for the primary endpoint. Study BP05 will also consider the following secondary analyses.

The RMDQ is a simple, sensitive, and reliable method to measure disability in patients with back pain. The RMDQ consists of 24 statements relating to the person's perceptions of back pain and associated disability based on:

- physical ability/activity
- sleep/rest
- psychosocial
- household management
- eating, and
- pain frequency.

Participants are asked if they feel the statement is descriptive of their own circumstance on that day. The total score is obtained by counting the number of “Yes” responses, ranging from 0 = no disability to 24 = maximal disability.

A Bayesian longitudinal MMRM analysis will be performed to evaluate the change from baseline to each postbaseline visit in the RMDQ total score. The model will utilize the cLDA so that a common mean is estimated at baseline. More details on this approach are provided in the CPMP SAP Version 5.

Information included in the model is shown in [Table BP05.7.2](#).

Table BP05.7.2. Information Included in Bayesian Longitudinal MMRM to Evaluate the Change from Baseline to Each Postbaseline Visit in the RMDQ Total Score

Categorical effects	
 The interaction of treatment and timepoint (constrained to estimate a common mean at baseline across treatments) Average baseline pain severity category (baseline NRS <7, baseline NRS ≥7) Presence of neuropathic pain (painDETECT ≥19, painDETECT <19) Pooled investigative site
Continuous covariates	
 None

Abbreviation: NRS = numeric rating scale.

Other Secondary Analysis

The proportion of participants in each treatment group meeting prespecified binary efficacy outcomes will be calculated for each postbaseline time point and will be used to compare treatment groups. The prespecified binary efficacy outcomes include the proportion of participants:

- with a reduction greater than or equal to 30%, 50%, and 70% from baseline as measured by the RMDQ score, and
- with at least a 3.5-point reduction from baseline in the RMDQ score.

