A Bayesian pseudo-likelihood-based categorical repeated measures model will be used to estimate the proportion of participants in each treatment group meeting the prespecified threshold for each postbaseline time interval up to Week 8. These estimates will be used to compare treatment groups. More details on this approach are provided in the CPMP SAP Version 5.

The model will include the categorical and continuous covariates described for the secondary analysis of RMDQ total score.

In addition, time to first treatment response from baseline based on the prespecified binary thresholds above will be assessed. Analyses will be conducted according to the time to event analyses specified in the CPMP SAP Version 5.

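### The RMDQ responder models take over a covariate list without baseline RMDQ, which gives up some precision and protection against chance imbalance unless CPMP SAP Version 5 adds the score

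*SAP*

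**What the plan says.** SAP section 7.10.3 defines four binary RMDQ outcomes: reductions of at least 30%, 50% and 70% from baseline, and participants "with at least a 3.5-point reduction from baseline in the RMDQ score". Table BP05.5.1 (SAP section 5.2) places them under Other Secondary. The proportions "will be calculated for each postbaseline time point and will be used to compare treatment groups". The model is a Bayesian pseudo-likelihood categorical repeated measures model, used to "estimate the proportion of participants in each treatment group meeting the prespecified threshold for each postbaseline time interval" up to Week 8.

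On covariates the rule is explicit: "The model will include the categorical and continuous covariates described for the secondary analysis of RMDQ total score". The list it points to is Table BP05.7.2, which contains:

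- treatment by timepoint, "constrained to estimate a common mean at baseline across treatments"
- "Average baseline pain severity category (baseline NRS <7, baseline NRS ≥7")
- painDETECT category (19 or above, below 19)
- pooled investigative site
- continuous covariates: none

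Of the total-score model the SAP says: "The model will utilize the cLDA so that a common mean is estimated at baseline". Of the responder model it says: "More details on this approach are provided in the CPMP SAP Version 5". SAP section 7.2 places the general adjustment strategy in that same master SAP, which was not available here.

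**The concern.** Table BP05.7.2 was written for a model that already uses baseline RMDQ. Under the cLDA the baseline score is one of the repeated outcomes, so it does not need to appear as a covariate. That reasoning does not carry over to a responder outcome. Nobody has a responder status at baseline, so the common-mean constraint has nothing to act on, and no other listed term carries the baseline score. The NRS category measures pain intensity, not disability, and is at best a partial substitute.

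So one RMDQ analysis accounts for baseline RMDQ, the four responder analyses built on the same scale do not, and no reason is given. With about 100 completers (125 × 0.80), chance differences in baseline RMDQ are to be expected. SAP section 7.7 would display such a difference, but the responder models would not correct for it. It can also push the thresholds in opposite directions. A participant who starts high has more room for a 3.5-point drop but needs a larger drop to reach 70%.

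**Working it through.** The plan gives no power, variance or responder rate for these endpoints, so there is no figure of its own to reproduce. The headcount checks: 125 × 0.80 = 100.

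**From the documents:** about 125 randomised, 80% completing (SAP section 6.2); the covariates of Table BP05.7.2; the four thresholds.

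**Assumed:** RMDQ mean, SDs, correlations and improvement; number of RMDQ visits and sites; allocation (redacted).

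**1. Large-sample calculation, no treatment effect.** RMDQ is an integer, so a reduction of 3.5 means 4 or more. A logistic model with NRS and painDETECT categories is fitted with and without baseline RMDQ. Variance reduction = 1 − (residual variance with) / (residual variance without). With baseline mean 10 to 12, baseline SD 5, mean improvement 2.5 and baseline-to-follow-up correlation 0.5 to 0.7, the results for the 3.5-point responder are:

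- follow-up SD 5: 8.0% to 16.7%
- follow-up SD 6: 2.7% to 10.5%

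A second calculation over 18 scenarios gave 8.7% to 15.8% and 2.9% to 10.0%. A wide grid (mean 8 to 14, baseline SD 4 to 6, follow-up/baseline SD ratio 0.9 to 1.3, correlation 0.3 to 0.7, improvement 1.5 to 3.5) gave 0.5% to 33%, with the middle 80% of scenarios at 4% to 21%.

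**2. Simulated trials with four postbaseline visits.** These had 125 randomised (63/62), 20% random dropout, baseline mean 11 and six sites. A repeated-measures logistic model with a weak prior stood in for the planned model, and the Week 8 difference was averaged over covariates. For the 3.5-point responder under the null, with variance reduction = 1 − (SD with / SD without)²:

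| Baseline / follow-up SD | Correlation | SD without | SD with | Variance reduction | Shift per 1-point imbalance, without (pct points) |
|---|---|---|---|---|---|
| 5 / 5 | 0.5 | 0.0944 | 0.0875 | 14.1% | 3.49 |
| 5 / 5 | 0.6 | 0.0949 | 0.0896 | 10.9% | 3.08 |
| 5 / 5 | 0.7 | 0.0951 | 0.0908 | 8.8% | 2.80 |
| 5 / 6 | 0.5 | 0.0938 | 0.0904 | 7.1% | 2.63 |
| 5 / 6 | 0.6 | 0.0942 | 0.0919 | 4.8% | 2.16 |
| 5 / 6 | 0.7 | 0.0954 | 0.0938 | 3.3% | 1.74 |

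With the covariate, the shift is at most 0.2. An 83/42 split gives 13.7% and 3.2%, where equal allocation gives 14.2% and 3.4% from unrounded SDs.

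**3. Likely imbalance.** SD of the baseline mean difference = 5 × √(1/63 + 1/62) ≈ 0.9 point for all randomised, and 5 × √(1/50 + 1/50) = 1.0 for completers. A one-SD imbalance among all randomised therefore moves the 3.5-point difference by 0.9 × 1.74 ≈ 1.6 to 0.9 × 3.49 ≈ 3.1 percentage points. At 100 completers the chance of an imbalance above 0.25 SD is about 0.21 (1:1) to 0.24 (2:1).

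**4. Power for an assumed 2-point effect.** Power = Φ(difference/SD − 1.96). At SD 5/5 and correlation 0.5 the difference is 14.7 percentage points with or without the covariate. Without: Φ(0.147/0.0944 − 1.96) = Φ(−0.40) ≈ 34%. With: Φ(0.147/0.0875 − 1.96) = Φ(−0.28) ≈ 39%. At SD 5/6 the gain is about 2 points (28 to 30%, 34 to 35%, 40 to 42%).

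**5. Percentage thresholds, four-visit model.** Variance reduction is −0.4% to 1.9% at 30%, −0.4% to 5.8% at 50%, and 1.4% to 10.5% at 70%. At 70% a 1-point higher baseline mean moves the difference by −0.89 to −2.07 percentage points, the opposite sign to the 3.5-point outcome.

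**6. Check under different assumptions.** Single visit, 100 participants, baseline mean 12, SDs 5 and 5.5, control change −3.5, correlation 0.3 to 0.7, 1:1 and 2:1. Omitting the score raised the variance of the 3.5-point difference by 6% to 30%. For the percentage thresholds the variance ratio without/with ran from 0.98 to 1.13. Baseline RMDQ correlated with response at 0.27 to 0.45 for 3.5 points and −0.33 to −0.02 for 70%. The null mean difference stayed within 0.004 of zero, and type I error was 0.035 to 0.059 without the score and 0.035 to 0.054 with it.

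**The case against.** The strongest objection is that the gap is not proven. The SAP refers to CPMP SAP Version 5 for details of this very model and for the general adjustment strategy, and that plan may add the score. This stands as a limit and is why the fix is conditional. It does not remove the point: the RMDQ outcomes are specific to this study, this SAP states their covariate rule itself, and a programmer following that rule would leave baseline RMDQ out.

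Three further points stand. These endpoints are low in the hierarchy of a proof-of-concept study with no multiplicity adjustment, and the mean RMDQ change, which does use baseline, is analysed separately. The gain is consistent only for the 3.5-point responder; at the 30% and 50% thresholds it may be nil or slightly negative. Every size rests on assumed inputs, and the simulated model only approximates the planned Bayesian one.

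It can also be said that adjusting for pain severity, neuropathic pain and site is an acceptable prespecified choice. It is, and the comparison is valid without baseline RMDQ. But the omission appears to come from reusing a list made for another type of model, and the better choice costs almost nothing.

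**Conclusion.** The point holds, as a modest matter of efficiency and robustness. On the text of this SAP the responder comparisons are not adjusted for baseline RMDQ. They are not biased and type I error is near nominal. For the 3.5-point responder, with baseline SD 5, follow-up SD 5 or 6 and correlation 0.5 to 0.7, the variance given up is roughly 3% to 17%. That is worth about 2 to 5 points of power for a 2-point effect. The benefit at 70% is smaller, and at 30% and 50% it is small or absent. The conclusion about the covariate list comes directly from the text; the sizes do not, and none should be read as an estimate for this trial. The whole point lapses if CPMP SAP Version 5 already includes the baseline score in the responder models.

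**What to change.** In SAP section 7.10.3, replace the cross-reference with a separate covariate list for the responder models, the same for all four thresholds: treatment by timepoint at postbaseline time points, baseline NRS category, painDETECT category, pooled site, and continuous baseline RMDQ total score. State that group proportions and their difference are averaged over the observed covariates, so that adding a covariate to a logistic-type model does not change the quantity reported. Align the text with CPMP SAP Version 5. If that SAP already adds the score, cite its text in 7.10.3 instead. Either way, settle this before unblinding, because a covariate added after an imbalance has been seen is less credible.

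The cost is about two sentences, one covariate and one averaging step in the programming. Baseline RMDQ is already to be summarised under SAP section 7.7, so no data are added. The downside is a small efficiency loss at some percentage thresholds: up to 0.4% in the four-visit simulation and about 2% in the single-visit one.

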7.11. Pharmacokinetic/Pharmacodynamic Methods

The plasma concentrations for LY3857210 will be reported graphically and summarized descriptively across the study visits.

Exploratory model-based analyses may be conducted to assess the relationship of LY3857210 plasma concentrations to efficacy and/or safety outcomes.

Approved on 27 Jun 2023 GMT
Additional analyses may be conducted, as needed.

Data from this study may be pooled with data from other studies.

7.12. Safety Analyses

The general analysis of safety has been described in the Study CPMP SAP Version 5. However, additional ISA-specific safety considerations are described in the sections below.

7.12.1. Extent of Exposure

Duration of exposure (defined as time since first dose of study treatment to last dose of study treatment in days) to study drug will be summarized by treatment group using descriptive statistics; the summary will also include the total exposure in patient years.

Duration of exposure (days):

Date of last dose during the double-blind treatment period – Date of first dose for the treatment period + 1.

Total exposure in patient years will be calculated as follows:

Summary of duration (days) of exposures for all participants in the treatment group / 365.25.

7.12.2. Adverse Events

The general analysis of AEs has been described in the CPMP SAP Version 5.

This ISA will report TEAEs separately for the entire 8-week double-blind period, the 2-week post-treatment period, and the entire 10-week study. For TEAEs in the double-blind period, the baseline will be prior to first dose date.

A PTEAE is defined as an event that first occurs or worsens in severity after double-blind treatment phase (after Visit 7) and on or before study discontinuation. This ISA will report PTEAEs for the post-treatment period, as they are important for assessing withdrawal or abuse liability potential. The MedDRA LLT will be used in the post-treatment-emergent computation. The maximum severity for each LLT during the double-blind treatment period (Visits 3 through 7) will be used as a reference.

The baseline of PTEAE is from the first dosing date to Visit 7. The post-treatment phase will be included as postbaseline for this analysis. While unusual, it is possible to have a missing severity for events. **CCI**

CCI

CCI

and PTEAEs will be determined by comparing with treatment period.

PTEAEs will be summarized by PT and by PT within SOC in participants who received LY3857210.

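### The PTEAE rule in SAP 7.12.2 leaves out a symptom that resolved on treatment and returns after Visit 7 under the same LLT at equal or lower severity

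*SAP*

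**What the plan says.** All of the rule is in SAP 7.12.2. A PTEAE is an event that first appears, or becomes more severe, after Visit 7 and no later than study discontinuation. The comparison window is the whole treatment period: "The baseline of PTEAE is from the first dosing date to Visit 7". The comparison is made term by term: "The MedDRA LLT will be used in the post-treatment-emergent computation". The severity to be exceeded is the worst one seen in that window: "The maximum severity for each LLT during the double-blind treatment period (Visits 3 through 7) will be used as a reference". The section gives the reason for reporting PTEAEs: "as they are important for assessing withdrawal or abuse liability potential".

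Two other sentences in the section matter here. The same two weeks are covered by a second report: "This ISA will report TEAEs separately for the entire 8-week double-blind period, the 2-week post-treatment period, and the entire 10-week study". A TEAE baseline is then given for only one of those periods: "For TEAEs in the double-blind period, the baseline will be prior to first dose date". The PTEAE table is planned for one arm: "PTEAEs will be summarized by PT and by PT within SOC in participants who received LY3857210".

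SAP 7.12.3 adds an assessment of abuse liability and withdrawal potential under a sponsor guidance that is not among the documents. General AE rules are left to CPMP SAP Version 5, which is also not supplied. Some text near the sentence on missing severity is redacted.

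**The concern.** A withdrawal table asks what changes when the drug stops. The natural reference is the participant's state at the end of treatment. The SAP instead uses the worst state at any time over eight weeks, including episodes that ended long before the last dose.

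Take a participant with a moderate headache in week 1 that clears within days, and another moderate headache three days after stopping. Under the visible rule the second headache is not a first occurrence and is not worse than the maximum, so it does not enter the table. A symptom that returns after stopping is one of the patterns a withdrawal assessment should be able to show. The stake is an undercount in a safety table that the SAP ties to withdrawal and abuse liability. The primary efficacy result is not affected.

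**Working it through.** The SAP states no figure for this rule, so there is none to reproduce. The check has three parts.

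**1. The rule applied case by case.** The first three rows concern an event that resolved before Visit 7 and returns under the same LLT.

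| Worst on treatment | After Visit 7 | PTEAE? |
|---|---|---|
| mild | mild | no |
| moderate | mild | no |
| mild | moderate | yes, worsened |
| none under this LLT | any severity | yes, first occurrence |

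No visible sentence exempts an event that had resolved. The omission therefore has two limits: same LLT, and severity no greater than the on-treatment maximum.

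**2. Effect on the LY3857210 count.** All inputs are assumptions; the documents give no AE rates.

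- p = on-treatment incidence of the LLT = 25%
- q = true post-treatment incidence = 12%
- w = share of recurrences that exceed the earlier maximum = 20%
- k = ratio of post-treatment risk in those with an earlier occurrence to the risk in those without = 1 or 3

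Risk without an earlier occurrence: q0 = q / (1 − p + kp). Counted incidence = q0(1 − p) + k·q0·p·w.

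- k = 1: q0 = 0.12. Counted = 0.12 × 0.75 + 0.12 × 0.25 × 0.2 = 0.090 + 0.006 = 9.6%. Loss = 2.4/12 = 20%.
- k = 3: q0 = 0.12/1.5 = 0.08. Counted = 0.08 × 0.75 + 3 × 0.08 × 0.25 × 0.2 = 0.060 + 0.012 = 7.2%. Loss = 4.8/12 = 40%.

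The lost share is kp(1 − w) / (1 − p + kp) and does not depend on q. Its sensitivity:

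| p | w | Loss, k = 1 | Loss, k = 3 |
|---|---|---|---|
| 25% | 0% | 25% | 0.75/1.5 = 50% |
| 25% | 20% | 20% | 40% |
| 25% | 40% | 15% | 0.45/1.5 = 30% |
| 5% | 20% | 4% | 0.12/1.10 = 10.9% |

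**3. A second model as a cross-check.** Instead of assuming w, let the on-treatment maximum and the post-treatment severity be independent with the same mild/moderate/severe distribution, and let post-treatment occurrence be independent of history. A recurrence is then dropped with probability (1 + sum of squared proportions)/2.

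- 50/40/10: (1 + 0.25 + 0.16 + 0.01)/2 = 71%
- 70/25/5: (1 + 0.49 + 0.0625 + 0.0025)/2 = 78%
- equal thirds: (1 + 0.333)/2 = 67%

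Multiplying the 71% by on-treatment incidence gives the share of all post-treatment events of that LLT left out: 1.4% at 2% incidence, 3.6% at 5%, 7.1% at 10%, 14.2% at 20% and 21.3% at 30%.

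In both models the loss is small for uncommon terms and grows with on-treatment incidence.

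**The case against.** The strongest reply is that the table is not the only view of these two weeks. TEAEs are reported for the post-treatment period and for the full ten weeks, and SAP 7.12.3 plans a separate withdrawal assessment. This stands in part. The general TEAE definition in SAP Section 3 compares with the pretreatment state. If that reference applies after Visit 7, the returning headache would appear among post-treatment TEAEs. But the pre-dose baseline is visibly attached to the double-blind period alone. A ten-week incidence table would not separate the return from the week 1 episode in the same participant. The sponsor guidance, the redacted text and CPMP SAP Version 5 could each add detail, and none can be checked. A reader might infer that the plan conceals withdrawal; the documents support only that one table leaves out a defined class of recurrence.

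A second reply is that a maximum-severity reference is a defensible choice, because it avoids labelling an episodic symptom as newly emergent when it merely comes round again. This stands. It is the reason to add a second count and keep the existing one.

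A third is that a 25% incidence for a single LLT is high. This also stands: at 5% the loss is 4% to 10.9% on the same assumptions.

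A reader might also infer that the rule shrinks a difference between LY3857210 and placebo. The visible text does not support this, because the PTEAE summary is planned for LY3857210 recipients only and has no between-arm difference to shrink.

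**Conclusion.** The point holds in a limited form. On the visible text, a symptom that resolved on treatment and returns after Visit 7 under the same LLT at equal or lower severity is left out of the PTEAE table. New LLTs and worse recurrences are captured, and capture among post-treatment TEAEs is uncertain.

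The size cannot be derived from the documents. On the assumed inputs the LY3857210 count drops by 20% (independent risk) to 40% (threefold risk) for a term with 25% on-treatment incidence, and by only a few percent for uncommon terms under independence.

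It is tempting to say that the loss is greatest for symptoms the drug itself causes. That follows only if withdrawal symptoms share LLTs with on-drug symptoms. A withdrawal symptom never seen on treatment is fully counted.

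This is a worthwhile improvement to a safety table and does not invalidate the plan.

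**What to change.** In SAP 7.12.2:

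1. Keep the maximum-severity table and report beside it a PTEAE count whose reference, per LLT, is the severity ongoing at the last dose. If nothing was ongoing under that LLT, count a recurrence as post-treatment-emergent. State whether counting starts from the last dose or after Visit 7, since the Protocol schedule of activities has no dose on the day of Visit 7.
2. Show the added count for both arms. The new reference will pick up some chance recurrences of common episodic symptoms, and placebo recipients show how many to expect.
3. State that the post-treatment TEAE report uses the pre-dose baseline.

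The cost is a few lines of SAP text and one derivation from AE start date, stop date and severity. No new data collection is needed.

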MMRM	mixed-effect model for repeated measures
NRS	numeric rating scale
participant	Equivalent to CDISC term “subject”: an individual who participates in a clinical trial, either as recipient of an investigational medicinal product or as a control
PD	pharmacodynamic
PDEP	preliminary data entry period
PK	pharmacokinetic
CCI	
PT	preferred term
PTEAE	Post-treatment-emergent adverse event
QTcF	Fridericia's corrected QT interval
RMDQ	Roland-Morris Disability Questionnaire
SAP	statistical analysis plan
screen	The act of determining if an individual meets minimum requirements to become part of a pool of potential candidates for participation in a clinical study.
SMQ	standardized MedDRA query
SOC	system organ class
TEAE	treatment-emergent adverse event: An untoward medical occurrence that emerges during a defined treatment period, having been absent pretreatment, or worsens relative to the pretreatment state, and does not necessarily have to have a causal relationship with this treatment.
ToE	totality of evidence
ULN	upper limit of normal
VAS	visual analog scale

4. Revision History

SAP Version 1 was approved on 20 January 2023 prior to unblinding data for Study H0P-MC-BP05 (BP05).

CCI

CCI

- Section 7.12.3: change SMQ to FMQ, which is FDA new standard.

CCI

- Section 7.18: added seizures in the totality of evidence of safety.

5. Study Objectives

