7.20. Clinical Trial Registry Analyses

Additional analyses will be performed for the purpose of fulfilling the CTR requirements.

Analyses provided for the CTR requirements include the following:

Summary of AEs, provided as a dataset that will be converted to an XML file. Both “Serious” AEs and “Other” AEs are summarized by treatment group and by MedDRA PT.

- A serious AE is an AE that is considered “Serious” whether or not it is a treatment emergent.

- An AE is considered in the “Other” category if it is both a TEAE and is not serious. For each “Serious” AE and “Other” AE, for each term and treatment group, the following are provided:
 - the number of participants at risk of an event
 - the number of participants who experienced each event term
 - the number of events experienced.
- Consistent with www.ClinicalTrials.gov requirements, “Other” AEs that occur in fewer than 5% of participants in every treatment group may not be included if a 5% threshold is chosen (5% is the minimum threshold).
- AE reporting is consistent with other document disclosures for example, the Clinical Study Report and manuscripts.

8. Unblinding Plan

The general unblinding plan is described in the CPMP SAP Version 5 and in the CPMP Blinding and Unblinding Plan Version 2. Unblinding considerations specific to Study BP05 are provided below.

PK/PD Analysis Planning

A limited number of prespecified individuals who are not part of the blinded study team and do not have direct site contact, data entry, or data validation responsibilities, may receive access to unblinded data, prior to an interim or final database lock, to initiate the PK and/or PK/PD model development processes. This will be described in the unblinding plan. Information that may unblind the study during the analyses will not be reported to study sites or blinded study team until the study has been unblinded.

9. References

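### The only summary stated in SAP 7.12.2 for post-treatment-emergent adverse events covers the LY3857210 arm, although their stated purpose, assessing withdrawal or abuse liability, calls for a placebo column

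*SAP*

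**What the plan says.** SAP 7.12.2 defines a PTEAE as an event that starts or becomes more severe after the double-blind treatment phase, that is, after Visit 7. The comparison is within the participant: "The maximum severity for each LLT during the double-blind treatment period (Visits 3 through 7) will be used as a reference". The definition is not limited to one arm. The section explains that PTEAEs will be reported for the post-treatment period "as they are important for assessing withdrawal or abuse liability potential". It closes with the only display it states: "PTEAEs will be summarized by PT and by PT within SOC in participants who received LY3857210".

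Other text bears on the point:

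- SAP 7.12.2 also says "This ISA will report TEAEs separately for the entire 8-week double-blind period, the 2-week post-treatment period, and the entire 10-week study". No arm is named.
- SAP 7.12.2 defers to the parent plan: "The general analysis of AEs has been described in the CPMP SAP Version 5".
- SAP 7.12.3 lists abuse liability and withdrawal potential as a further adverse event topic, to be handled under a sponsor guidance that it names but does not reproduce.
- Protocol 4.1 describes the post-treatment follow-up as double-blind and requires one visit, Visit 801, about two weeks after Visit 7 or the early discontinuation visit. The requirement applies to participants in general. The Schedule of Activities (Protocol 1.3) includes adverse event collection.

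**The concern.** A PTEAE is a before-and-after measure in one person. Some participants will report something new or worse in the two weeks after stopping any capsule, placebo included, for example through intercurrent illness or a return of pain. To read such events as a sign of withdrawal, one needs to know how often they occur after stopping placebo. The trial has a concurrent, randomised, still-blinded placebo group followed over the same interval, and the stated table leaves it out.

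At stake is the interpretation of one safety display. A reader of that table would see which preferred terms occur after LY3857210 is stopped, but not whether they exceed the placebo background.

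**Working it through.** **Text check.** The claim itself contains no figure, so the first step is to compare what is stated with what is available.

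1. Purpose: withdrawal or abuse liability (SAP 7.12.2).
2. Stated display: by preferred term, and by preferred term within system organ class, for LY3857210 recipients (SAP 7.12.2). The sentence is complete and legible. The redacted text in that section follows the remark on missing severity and ends before this sentence.
3. Other mentions: apart from 7.12.2, PTEAE appears only in the SAP abbreviation list. Neither document states a placebo or by-arm PTEAE summary.
4. Data: the double-blind follow-up to Visit 801 applies to both arms (Protocol 4.1), so placebo PTEAEs can be derived under the same rule.

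The restriction to one arm is therefore stated, and the data that would lift it are already being collected.

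**How precise would the comparison be?** The documents give about 125 randomised participants and about 80% completing double-blind treatment (Protocol 9.5, SAP 6.2), so 125 × 0.80 = 100. The allocation ratio is redacted and no PTEAE rate is given. Both are therefore assumptions here: 1:1, 2:1 or 1:2, and a rate of 5%, 10% or 20% in each arm for having any PTEAE.

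The 95% half-width for a difference in proportions is 1.96 × √[p(1 − p)(1/n₁ + 1/n₂)].

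For example, with p = 0.10 and 62/63: 1.96 × √[0.09 × (1/62 + 1/63)] = 1.96 × √0.002880 = 0.1052, or 10.5 points.

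| Arm sizes | p = 5% | p = 10% | p = 20% |
|---|---|---|---|
| 62/63 (1:1, all 125) | 7.64 | 10.52 | 14.03 |
| 83/42 or 42/83 (2:1 or 1:2, all 125) | 8.09 | 11.13 | 14.85 |
| 50/50 (1:1, 100 contributing) | 8.54 | 11.76 | 15.68 |
| 67/33 or 33/67 (2:1 or 1:2, 100 contributing) | 9.08 | 12.5 | 16.67 |

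Entries are percentage points. As a check on the approximation, the Newcombe interval at 10% in both arms with 62/63 is −11.2 to +11.2, close to ±10.5. The range is about ±8 to ±17 points.

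These figures concern the proportion with any PTEAE. The SAP's table is by preferred term, where rates may be much lower and the normal approximation poorer. The figures show that a placebo column would be descriptive; they do not measure the term-level table.

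**The case against.** The strongest reply is that this SAP is a supplement. General adverse event analysis is deferred to CPMP SAP Version 5, and abuse and withdrawal potential is assigned in SAP 7.12.3 to a sponsor guidance. Either may already require a by-arm PTEAE table. This stands. It limits the point to what is stated here, and a reader who infers that the sponsor will not look at placebo PTEAEs goes further than the documents allow.

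The reply can add that post-treatment TEAEs are reported with no arm restriction and may supply placebo context. This stands too. One might answer that those TEAEs use a different reference, because the SAP's definitions describe a TEAE as "having been absent pretreatment, or worsens relative to the pretreatment state". The visible text does not settle that. SAP 7.12.2 fixes a pre-dose baseline only for TEAEs in the double-blind period, shows none for the post-treatment report, and is partly redacted at the rule for determining these events. If the baseline were the treatment period, that report would come close to the missing comparison.

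A reader might also infer a drafting convention, because exposure "to study drug will be summarized by treatment group using descriptive statistics" (SAP 7.12.1) and registry adverse events "are summarized by treatment group and by MedDRA PT" (SAP 7.20), so that wording without the phrase would mean one arm. The documents do not support this. The sections on the neurological exam, laboratory tests, vital signs, ECG and suicidality (SAP 7.12.4 to 7.12.8) evidently cover both arms without using it. The case rests on the explicit restriction in the PTEAE sentence alone.

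Last, the consequence is small. Placebo adverse events are collected in any case and a column can be added at reporting. Withdrawal is not among the key safety events in SAP 7.18, and convulsion, the event of special interest (Protocol 8.3.3), has its own seizure analysis. All of this stands and sets the weight of the point.

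**Conclusion.** The point holds as a minor one. The one PTEAE summary that SAP 7.12.2 states is limited to LY3857210 recipients, and by itself it cannot serve the purpose given for it, because it carries no placebo rate under the same definition.

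The conclusion is that a placebo display is not stated here. It is subject to three unknowns: the content of CPMP SAP Version 5, the content of the sponsor guidance, and the redacted text with the baseline for post-treatment TEAEs. No primary analysis, decision rule or error rate is affected.

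The added comparison would be imprecise, at about ±8 to ±17 points for any PTEAE under the assumed rates and allocations. It should be read as a description and not as a test.

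**What to change.** In the last sentence of SAP 7.12.2, replace the restriction to LY3857210 recipients with a summary by treatment group (LY3857210 and placebo), keeping the same levels of preferred term and preferred term within system organ class, and say that the comparison is descriptive. If CPMP SAP Version 5 or the sponsor guidance already specifies this, cite the section instead.

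The cost is one sentence and one table column, or one cross-reference. No new data or visits are needed.
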